4.3. Primary Efficacy Endpoints

The two co-primary efficacy endpoints are the decrease in anti-fXa activity following and examet treatment and the achievement of hemostatic efficacy. Anti-fXa activity will be evaluated at baseline, EOB, and at EOI, 4, 8, and 12 hours post-treatment. Anti-fXa activity will be expressed as ng/mL for apixaban, rivaroxaban, and edoxaban, and in IU/mL for enoxaparin.

The anti-fXa activity will be evaluated for the co-primary endpoint using percent change from baseline to on-treatment nadir.

The median percent change and 95% confidence intervals will be calculated separately for each FXA inhibitor.

The following variables will be calculated:

- On treatment Nadir: The on treatment nadir is the minimum value observed during treatment administration (i.e., minimum of EOB and EOI).
- Change from Baseline to On treatment Nadir: Change from baseline to On treatment Nadir is the reduction in anti-fXa activity from baseline to the minimum value during treatment administration (i.e., minimum value of EOB and EOI).
- Percent Change from Baseline to On treatment Nadir: The percent change from baseline
 to On treatment Nadir is the ratio between the Change from Baseline to On treatment
 Nadir, and the baseline, multiplied by 100.
- Percent Change from Baseline: The percent change from baseline is the ratio between the maximum change from baseline and the baseline, multiplied by 100.
- Percent Change from Baseline to EOI: The percent change from baseline to the EOI is the ratio between the Change from baseline to the EOI and the baseline, multiplied by 100.
- 12 hour Nadir: The 12 hour nadir is the minimum value observed post start of treatment evaluations (i.e., EOB to 12 hours post start of andexanet treatment).
- Area Under the Curve (AUC) for anti-fXa activity at each time point up to the 4 hours post end of infusion. The AUC will be calculated using trapezoid rule as follows:
 - Trapezoidal area calculation = ½ * (PCAFXa(x2) + PCAFXa(x1)) * (Time(x2) Time(x1)), where PCAFXa = Anti-fXa; X1 is first or earlier time point and X2 is second time point.

Hemostatic efficacy will be determined by the blinded EAC as excellent, good, poor/none, not evaluable due to administrative reasons, or not evaluable due to clinical issue based as described

in the study protocol and Endpoint Adjudication Charter. Hemostatic efficacy will be presented as follows:

- Excellent
- Good
- Poor/None
- · Not Evaluable

Effective hemostasis will be further defined as:

- 0 = patients with hemostatic efficacy rated by the EAC as poor/none
- 1 = patients with hemostatic efficacy rated by the EAC as excellent or good.
- 2 = Not evaluable due to non-administrative reason
- 3 = Not evaluable due to administrative reason.

4.4. Secondary Efficacy Endpoint

The secondary objective is to assess the relationship between anti-fXa activity and hemostatic efficacy. The anti-fXa activity will be evaluated as nadir (on treatment nadir), 12 hours nadir, absolute change from baseline, percent change from baseline, and the AUC for the anti-fXa activity as described above for the primary endpoint.

Hemostatic efficacy will be based on the outcome of adjudication as described above for the primary endpoint.

4.5. Other Efficacy Endpoints

4.5.1. Free Fraction of the FXa Inhibitor

The free fraction plasma concentration (ng/mL; also called the unbound plasma fraction) of apixaban, rivaroxaban, and edoxaban will be evaluated at Baseline (prior to andexanet treatment), and at EOB, EOI, 4, 8, and 12 hours after the EOI. In addition, % Protein Binding and Total Plasma Concentration (ng/mL) will be determined.

Change and percent change from baseline in free fraction of the inhibitor to the minimum value during and exanet treatment administration (i.e., minimum value between (EOB and EOI), and to each time point will be calculated. Values reported as <0.03125 will be replaced with 0.03125.

4.5.2. Tissue factor pathway inhibitor (TFPI)

TFPI parameters were collected, starting with Protocol Amendment 4 at baseline, EOI, 4, 8, 12, 24, 48, and 72 hours, and 7 days post and exanet treatment. TFPI Activity, Free TFPI antigen, and Total TFPI antigen will be determined.

Values < 0.2 will be replaced with $\frac{1}{2}$ of LLOQ (i.e., 0.1). TFPI parameters will also be summarized as part of the safety analysis.

4.5.3. Thrombin Generation

Thrombin generation plasma samples were taken at Baseline, 8, 12, with additional samples (EOB, EOI, 4, 18, 24, 72 hours post infusion, and Day 30) collected starting with Protocol Amendment 4. Thrombin generation will be performed at a Central Laboratory. Five parameters related to thrombin generation are measured: Endogenous Thrombin Potential (ETP), peak height, time to peak height, lag time, and velocity index. Also, non-tissue factor ETP, lag time, peak height, time to peak height, and velocity index will be evaluated. Endogenous Thrombin Potential (ETP).

Endogenous Thrombin Potential (ETP) and non-tissue factor ETP are prospectively identified as the primary measure for thrombin generation.

Change and percent change from baseline for Endogenous Thrombin Potential to peak concentration and for non-tissue factor ETP will be calculated, and change from baseline for each time point will be calculated. Peak is the largest value between end of andexanet bolus and ending of infusion for each subject. For values identified by the lab as "BMC" will be replaced with zeros. Values identified as "AMC" will be replaced with blank (i.e., missing).

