11.7. Safety Endpoints and Summaries

11.7.1. Adverse Events

Safety will be assessed by examination of survival status, AEs (including central adjudication of TEs and deaths), vital signs, clinical laboratory measurements, thrombin generation, TFPI levels, antibodies to and examet, FX, and FXa.

Vital signs will be summarized using actual values and change from baseline at pre-specified time points for each treatment group. Descriptive statistics, including threshold-based outlier analyses, will be presented.

The presence of antibodies (anti-andexanet, anti-fX, anti-fXa, and/or neutralizing antibody activity) will be summarized in a listing.

Treatment-Emergent Adverse Events (TEAEs), including preferred terms defined by the Medical Dictionary for Regulatory Activities (MedDRA), will be summarized by system organ class. Arterial and venous thrombotic events and serious and severe infusion reactions, considered AEs of special interest, will be separately summarized.

The number of events, the number of patients, and the percentage of patients who experienced at least one TEAE will be presented. TEAEs that are considered by the investigator to be related to the andexanet; TEAEs that lead to early withdrawals; and serious TEAEs will be summarized in the same manner. Frequent TEAEs, including preferred terms with an incidence rate of $\geq 5\%$, will also be summarized.

Concomitant medications will be coded using the WHO Drug Dictionary.

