 the value will be taken as LLOQ threshold value.
- For plasma concentrations that are higher than the upper level of quantification (ULOQ) then the value will be taken as ULOQ threshold value.

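### Thrombin-generation values flagged BMC become zero and those flagged AMC become missing: percent change is undefined from a zero baseline and, if AMC means above range, the highest values are lost

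*SAP*

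**What the plan says.** SAP 4.5.3 covers five thrombin-generation parameters (ETP, peak height, time to peak, lag time, velocity index), each in a tissue-factor and a non-tissue-factor assay. ETP is the leading measure. On derivation it says: "Change and percent change from baseline for Endogenous Thrombin Potential to peak concentration and for non-tissue factor ETP will be calculated". It adds: "Peak is the largest value between end of andexanet bolus and ending of infusion for each subject". SAP 5.15.1.2 repeats this, with medians and distribution-free confidence intervals, and summarises the other parameters by time point.

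The same paragraph of SAP 4.5.3 ends with the substitution rule. Values flagged BMC "will be replaced with zeros"; values flagged AMC "will be replaced with blank (i.e., missing". Neither flag is explained in the text or in either abbreviation list. No assay limits are given, and no rule covers a baseline that has been set to zero.

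For other measurements the SAP substitutes a limit or half of it:

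- Anti-fXa is set to 950 or 4.0 ng/mL, or to 0.10 IU/mL at the lower end for enoxaparin (5.5.1).
- Free fraction is set to 0.03125 (4.5.1), TFPI to half its lower limit (4.5.2), and anti-IIa below 0.04 to 0.02 (4.5.5).
- A result recorded as greater or less than x is taken as x (5.5.4).
- In 5.9, "For plasma concentrations that are higher than the upper level of quantification (ULOQ) then the value will be taken as ULOQ threshold value", with the matching rule at the lower limit.

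Protocol 11.5.4 makes thrombin generation an exploratory efficacy endpoint. Protocol 11.7.1 still lists it among the safety assessments: "clinical laboratory measurements, thrombin generation, TFPI levels".

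**The concern.** Two things go wrong, and the first does not depend on what the flags mean.

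A planned percent change has its denominator set to zero by rule. Patients with a BMC baseline therefore have no value for that summary. If BMC means below range, they are the patients whose thrombin generation was most suppressed, which is where reversal is of most interest.

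If AMC is the upper counterpart of BMC, making it missing is not neutral: values are removed because they are high. The derived peak is a maximum, so it is especially exposed to this. The ETP rise would be understated, and a high reading would be absent from the by-time-point summaries in which an overshoot should show.

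**Working it through.** **No plan figure to reproduce.** The documents give no assay limits, flag frequency or power statement for thrombin generation. The rule itself is checked first, then the possible scale.

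**1. Zero baseline.** Percent change is 100 × (post − baseline)/baseline, the form written out in SAP 5.13.1. With baseline = 0 it is 100 × (post − 0)/0, which is undefined. Absolute change is post − 0 = post, so the patient stays in that summary. If BMC means below range, post − 0 exceeds the true change by at most the lower limit.

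**2. AMC and the peak, read as above range.** The peak is the larger of the end-of-bolus (EOB) and end-of-infusion (EOI) values.

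- One flagged: the peak becomes the other value, which is lower.
- Both flagged: there is no peak, and SAP 5.9 keeps only patients with data at baseline and follow-up, so the patient is lost.

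**3. Scale for the peak.** All inputs are assumptions: 200,000 simulated patients; log-normal ETP; baseline median 400 with log-SD 0.6; EOB and EOI medians 1000 with log-SD 0.5; correlation 0.5 on the log scale. Before any flagging, the median peak is 1215 and the median percent change +205%.

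| On-treatment samples AMC | Patients lost | Kept, peak lowered | Median peak, blanked / capped | Median % change, blanked / capped |
|---|---|---|---|---|
| 2% | 0.3% | 3.3% | 1204 / 1215 | 198 / 203 |
| 5% | 1.2% | 7.6% | 1177 / 1215 | 190 / 199 |
| 10% | 3.2% | 13.5% | 1129 / 1215 | 179 / 193 |
| 20% | 8.7% | 22.6% | 1034 / 1215 | 162 / 179 |
| 30% | 15.7% | 28.6% | 943 / 1215 | 147 / 163 |

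At 10%, blanking affects 3.2 + 13.5 = 16.7% of patients and lowers the median peak by 1215 − 1129 = 86, or 7%. Capping leaves the median peak unchanged because fewer than half of patients exceed the limit, even at 30% (15.7 + 28.6 = 44.3%). Capping recovers only part of the percent change.

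**4. Scale for the zero baseline.** Same assumptions, with BMC at baseline in 2 / 5 / 10 / 20 / 30% of patients. Median percent change among those still defined is +201 / 196 / 188 / 172 / 159%. With the lower limit substituted it is +205 / 203 / 200 / 189 / 175%.

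**5. Scale at a single time point.** Deleting the top fraction f of a normal variable, with z its (1 − f) quantile, shifts the mean by −φ(z)/(1 − f) and the median to Φ⁻¹((1 − f)/2). For f = 5% these are −0.109 and −0.063 SD; for f = 10%, −0.195 and −0.126 SD.

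**6. Lag time and time to peak.** The rule sits in a paragraph about ETP but states no limit to ETP.

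- If it applies to the time parameters and flags are per parameter, a BMC lag is a very short one. Zero then errs in the right direction, and a very long lag is AMC and blanked.
- If one flag marks a whole curve with no measurable thrombin generation, zero would score that sample as immediate.

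The documents do not say which applies.

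**The case against.** The strongest reply is that little rests on this. The endpoint is exploratory, with no threshold or hypothesis test, and neither primary endpoint nor the secondary objective uses it. Absolute change and medians are already planned, so a patient with a zero baseline is not lost altogether. SAP 5.17.1.4 records that Amendment 4 moved thrombin generation from safety to efficacy, and SAP 5.16 plans no safety analysis of it. The limit rule in SAP 5.9 is written for plasma concentrations, whereas ETP is in nM*min. All of this stands and bounds the importance. It does not supply a percent change from a zero baseline or explain why this assay alone uses zero and blank. Protocol 11.7.1 and 11.7.4 still include thrombin generation in the safety and laboratory summaries.

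A reader might go further in three ways that the documents do not support.

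- That the top responses are certainly discarded. This needs AMC to mean above range, which is the natural reading but nowhere stated.
- That the rule reverses the meaning of lag time and time to peak. Under a below/above-range reading applied per parameter it does not. Always ranking a BMC lag as longest could itself reverse the direction.
- That the rule flatters the drug. Blanking high on-treatment ETP lowers the apparent reversal, so on efficacy it works against andexanet.

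**Conclusion.** The concern holds in a limited form. Whatever the flags stand for, SAP 4.5.3 makes percent change in ETP and non-tissue-factor ETP undefined for any patient with a BMC baseline, and gives no fallback. If AMC means above the measurable range, blanking is informative missingness. It understates the ETP rise and could conceal high thrombin generation, and it departs from how the SAP treats its other assays. The size cannot be stated for this trial, because flag frequency and assay limits are not in the documents; the figures above show scale under assumed inputs only. The effect is confined to exploratory and descriptive summaries. It is still worth correcting, because it is a stated rule that gives a worse answer than the SAP's own usual one, and the change is cheap.

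**What to change.** In SAP 4.5.3:

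1. Confirm with the central laboratory, and write down, what BMC and AMC mean, the reporting limits, and whether a flag applies to a sample or to a single parameter.
2. If they are range flags, set AMC to the upper reporting limit and BMC to the lower limit, not zero, for ETP, peak height and velocity index.
3. Where the baseline is flagged, rely on absolute change and say so.
4. For lag time and time to peak, do not apply zero or blank by default. If flags are per parameter, cap at the respective limit. If a flag marks a curve with no measurable thrombin generation, treat the time as not reached.
5. Tabulate the number flagged, by type, at each time point.

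The cost is SAP wording, some programming and one enquiry to the laboratory. Sites are not affected and no new samples are needed. SAP 1.0 refers to 477 locked patients, so the change should be dated in the SAP's list of changes.

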4.5.4. Antithrombin III (ATIII)

ATIII was collected starting Protocol Amendment 4 at baseline, EOI, 4, 8, 12, 24, 48, and 72 hours, and 7 days post and examet treatment.

4.5.5. Anti-factor IIa Levels

Anti-factor IIa levels (pre- and post-administration of andexanet will only be collected for patients treated with enoxaparin. Values reported as < 0.04 will be replaced with 0.02.

4.5.6. Glasgow Coma Score (GCS)

The GCS will be evaluated only for ICH patients. Ideally the initial assessment would be made in the pre-morbid state, which is not possible within the context of this study. Therefore, the assessment will be performed at baseline, at 1 hour, 12 post the end of andexanet infusion, and at Day 30 follow-up. Each patient will be rated for all three domains (i.e., Eye Opening, Verbal Response, and Best Motor Response) in a scale of 1 to 6 as described below:

Score	Criterion
Eye Openi	ng
4	Open before stimulus
3	After spoken or shouted request
2	After fingertip stimulus
1	No opening at any time, no interfering factor
NT	Closed by local factor
Verbal Res	ponse
5	Correctly gives name, place, and date
4	Not orientated but communication coherently
3	Intelligible single words
2 Only moans/groans	
1 No audible response, nom interfering factor	
NT	Factor interfering with communication
Best Motor	Response
6	Obey 2-part request
5	Brings hand above clavicle to stimulus on head/neck
4	Bends arm at elbow rapidly but features not predominantly abnormal
3 Bends arm at elbow, features clearly predominantly abnorm	
2	Extends arm at elbow
1	No movement in arms/legs, no interfering factor
NT	Paralyzed or other limiting factor

NT = Not testable

The individual scores from each item are summed in order to calculate a patient's total GCS score. The maximum possible score is 15, with the minimum score being of 3.

Note to programmer, because the "NT" can be analyzed in multiple ways, individual scores for eye opening, verbal and motor response should be presented.

4.5.7. Modified Rankin Score (mRS)

The mRS will be evaluated only for ICH patients. Ideally the initial assessment would be made in the pre-morbid state, which is not possible within the context of this study. Therefore, the assessment will be performed at baseline, at 1 hour, 12 post the end of andexanet infusion and at Day 30 follow-up. The scale runs from 0 to 6, running from perfect health without symptoms (0) to death (6).

- 0 No symptoms at all.
- 1 No significant disability. Able to carry out all usual duties and activities, despite some symptoms.

- 2 Slight disability. Able to look after own affairs without assistance, but unable to carry out all previous activities.
- 3 Moderate disability. Requiring some help, but able to walk without assistance.
- 4 Moderately severe disability. Unable to attend to own bodily needs without assistance, and unable to walk unassisted.
- 5 Severe disability. Requires constant nursing care and attention, bedridden, incontinent.
- 6 Dead.

mRS will be further defined at each time point as follows:

- 1 = for patients with of zero to 2, inclusive, and
- 0 = for patients with score greater than 2.

4.5.8. National Institutes of Health Stroke Scale (NIHSS)

The NIHSS will be evaluated only for ICH patients. Assessment will be performed at baseline, at 1 hour, 12 post the end of and exanet infusion and at Day 30 follow-up. The NIHSS is composed of 11 items, each of which scores a specific ability between a 0 and 4. For each item, a score of 0 typically indicates normal function in that specific ability, while a higher score is indicative of some level of impairment. The overall severity of stroke can be interpreted as follows:

NIHS Score	Stroke Severity	
0	No stroke symptoms	
1-4	Minor stroke	
5-15	Moderate stroke	
16-20	Moderate to severe stroke	
21-42	Severe stroke	

The individual scores from each item are summed in order to calculate a patient's total NIHSS. The maximum possible score is 42, with the minimum score being of 0. For handling of missing values, refer to Section 5.5.3 of this document.

4.5.9. ICH Score

The ICH Score is a clinical grading scale designed for risk stratification of patients after acute non traumatic intracerebral hemorrhage (ICH) [2]. The total ICH Score (is the sum of the points of the various characteristics as indicated below.

Component	Levels	ICH Score Points	
GCS	3 -4	2	
	5 - 12	1	
	13 - 15	0	
ICH Volume	$\geq 30 \text{ cm}^3$	1	
	$< 30 \text{ cm}^3$	0	
Intraventricular Hemorrhage (CRF#160)	Yes	1	
5000 92 5000	No	0	
Infratentorial origin of ICH (CRF#160)	Yes	1	
	No	0	
Age	≥ 80 years	1	
	< 80 years	0	

ICH Volume is calculated using the formula ABC/2, where A is the greatest diameter of the hematoma on the slice with the largest diameter, B is the diameter of the hematoma in the axis perpendicular to A, and C is the number of axial slices in which the hematoma is visible, multiplied by the slice thickness. See CRF #160 for 'Intra-ventricular hemorrhage' 'Intracerebral hemorrhage' 'Intracranial hemorrhage' for hematoma volume.

For Infratentorial origin of ICH reply yes, if faobj='Infratentorial bleed' and FAORRES='Yes'.

4.6. Safety Endpoints

4.6.1. Exposure

- Planned Andexanet Dose
- Andexanet Dose Received
- Was the Treatment Modified (yes, no)
- Reason for Treatment Modification:
 - Treatment was not Modified
 - Withdrawal of Consent
 - Intolerable AE/SAE that cannot be ameliorated by appropriate medical intervention
 - AE/SAE that in the Investigator's opinion would lead to undue risk
 - o Infusion Reaction
 - Other
- Treatment Modification
 - Treatment was not Modification

- Rate Increased
- Rate Decreased
- Discontinued
- Interrupted

4.6.2. Infusion Reaction (CR # 054)

- Patient had an Infusion Reaction (yes, no)
- Duration of the Infusion Reaction (minutes)
- Time from Start of Andexanet Administration to the Reaction (minutes)
- Infusion Reaction Symptom
- Was the Treatment Modified (yes, no)
- Treatment Received for Infusion Reaction

4.6.3. Use of Red Blood Cell Transfusions

• Were Blood Products and Hemostatic Agents used Post Treatment (yes, no)

4.6.4. Re-bleeding

Re-bleeding is defined as bleeding from the same or another anatomical site in the patient within 24 hours of initial and exanet treatment and after achieving initial good/excellent hemostasis.

Re-bleeding will be adjudicated by the EAC. The following variables will be analyzed:

- Did Re-bleeding Occur (yes, no)
- Site of Re-bleeding
- Start Date/Time of Re-bleeding
- Stop Date/Time of Re-bleeding
- Time to Re-bleeding: Numbers of days/hours from date time of first dose of andexanet treatment to the time of Re-bleeding.
- Treatment Received for Re-Bleeding
- Coagulation Factor Transfusion (yes, no)
- Hemostatic Treatments (yes, no)
- Packed Red Blood Cell Transfusion (yes, no)
- Use of Colloids and Crystalloids (yes, no)
- Other blood/coagulation Related Treatment (yes, no)

4.6.5. **Death**

- Did the Patient Die (yes, no)
- Date/time of Death
- Time to Death: Number of days/hours from inform consent to death.
- Cause of Death; Adjudicated cause of death will be first grouped as cardiovascular or Non-cardiovascular as adjudicated by the EAC. In addition, the sub-category as presented in CR#099 for Cardiovascular or non-cardiovascular reason need to be specified.
- Death Preceded by Myocardial Infarction, Ischemic Stroke (note to programmer: ischemic stroke sometimes was reported as Embolic Stoke), Deep Vein Thrombosis, Pulmonary Embolism, and/or Arterial Systemic Embolism.

4.6.6. Hospitalization

Hospital Length of Stay (LOS): Duration of the index hospitalization. The following steps will be followed to calculate the LOS:

- The LOS will be calculated as the discharge date/time minus the admission date/time plus 1.
- If patient admission time and the discharge time is missing and the dates are the same, the LOS will assumed to be 1 day.
- If patient admission time and the discharge time is missing and the dates are not the same, the LOS will calculated using the date portion of the dates plus 1.
- If the discharge date is missing, and no new admission date, the date of the 30-day visit, the date of death, or 37 days after enrollment (whichever is earliest) will be imputed as the discharge date and calculate the LOS for the given stay.
- If a patient has withdrawn consent, exclude the patient from analysis of hospital LOS.

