5.16.4. Thrombotic Events

Potential Thrombotic Events (TEs) will be submitted by each Investigator for adjudication by the EAC using definitions pre-specified in the EAC Charter. The proportion of patients in the safety population who are adjudicated to have a TE by the independent EAC will be summarized. An exact 95% CI will be reported. Analysis will be performed for the safety patient population, by age category, sex, region, FXa inhibitor, bleeding type, andexanet dose, andexanet manufacturing process, medical history (i.e., atrial fibrillation (AF), Ischemic Stroke or Transient Ischemic Attack (CVA/TIA), Venous Thrombotic Event (VTE), or Cancer); and the type of TE (i.e., Ischemic Stroke (CVA), Myocardial Infarction (MI), Deep Vein Thrombosis (DVT), Pulmonary Embolism (PE), Arterial Systemic Embolism (ASE), and Transient Ischemic Attack (TIA). Also, the age, sex, FXa inhibitor, type of bleeding, previous history of TE, hospital length of stay and deaths for patients with and without thrombotic events will be compared.

An additional summary of possible TEs will be presented using a broader definition of TEs as recommended by FDA. See Section 4.6.8 for further details on the selection of events. The proportion of patients in the safety population who have a TE by this broader definition will be summarized. An exact 95% CI will be reported.

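### Hospital length of stay adds 1 to a date/time difference, so timed stays are neither elapsed time nor calendar days, and stays without times follow a different count

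*SAP*

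**What the plan says.** SAP 4.6.6 introduces the variable as "Hospital Length of Stay (LOS): Duration of the index hospitalization" and then gives a list of rules.

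- General rule: "The LOS will be calculated as the discharge date/time minus the admission date/time plus 1". The unit of the 1 is not given.
- Both clock times missing, same date: "If patient admission time and the discharge time is missing and the dates are the same, the LOS will assumed to be 1 day".
- Both clock times missing, different dates: if "the dates are not the same, the LOS will calculated using the date portion of the dates plus 1".
- Discharge date missing with no new admission: the earliest of the 30-day visit, death, or "37 days after enrollment (whichever is earliest) will be imputed as the discharge date and calculate the LOS for the given stay".
- Patients who withdrew consent are left out.

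LOS is used in SAP 5.16.4, where "hospital length of stay and deaths for patients with and without thrombotic events will be compared". It sits under the safety endpoints heading of the SAP (4.6) but is not among the safety endpoints in Protocol 11.5.5.

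**The concern.** Adding 1 is the usual device when whole dates are subtracted and both end days are to count. It has no such role when clock times are subtracted, because that difference already measures the whole interval. The general rule therefore mixes two conventions. It keeps the fraction of a day, as an elapsed time would, and adds a full day, as a calendar count would. The result is neither.

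The missing-time rules, by contrast, are a plain inclusive calendar count. Two patients with identical stays can be given different values solely because one site recorded clock times and the other did not. At stake are the LOS figures in the study report, above all for short stays; Protocol 3.5 expects patients to remain in hospital for at least 12 hours, so short stays are possible.

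**Working it through.** **Inputs.** All rules are from SAP 4.6.6. The documents give no distribution of LOS, of times of day, or of missing times, so the average gaps below rest on assumed times of day.

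**Notation.** D is the discharge date minus the admission date in whole days. f_adm and f_dis are the admission and discharge times as fractions of 24 hours. Elapsed time is E = D + f_dis - f_adm.

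**The plan's own figure.** For a same-date stay without times, D + 1 = 0 + 1 = 1 day. This reproduces the only LOS value that the SAP states and shows that the unit is days.

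**Two rules for one stay.**

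- Timed rule: E + 1.
- Date-only rule: D + 1 = E + 1 + (f_adm - f_dis).

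| Stay | D | E | Timed, E + 1 | Date-only, D + 1 | Date-only minus timed |
|---|---|---|---|---|---|
| 10:00 to 22:00, same day | 0 | 0.5 | 1.5 | 1 | -0.5 |
| Day 1 08:00 to day 3 20:00 | 2 | 2.5 | 3.5 | 3 | -0.5 |
| Day 1 22:00 to day 9 10:00 | 8 | 7.5 | 8.5 | 9 | +0.5 |
| 01:00 to 23:00, same day | 0 | 0.917 | 1.917 | 1 | -0.917 |
| 23:00 to 01:00 next day | 1 | 0.083 | 1.083 | 2 | +0.917 |
| Exactly 48 h | 2 | 2 | 3 | 3 | 0 |

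**Level.** The timed value exceeds E by exactly 1 day (24 h) in every row. As a share of a true stay of L days this is 100/L percent: 100% at 1 day, 20% at 5, 10% at 10 and 3.3% at 30.

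**Mismatch.** The two rules differ by f_adm - f_dis, which lies strictly between -1 and +1 day. The +1 appears in both and drops out of the difference.

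- Times uniform over the day: mean gap 0.5 - 0.5 = 0.00 day; SD = sqrt(1/12 + 1/12) = 0.41 day.
- Admissions uniform, discharges uniform between 10:00 and 18:00: mean gap 12/24 - 14/24 = -0.08 day (about -2 h); SD = sqrt(1/12 + (8/24)²/12) = 0.30 day.

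A simulation of 1,000,000 stays gave the same means and SDs.

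**Date-only stays against elapsed time.** D + 1 - E = 1 + (f_adm - f_dis). The mean is 1.00 day in the first pattern and 0.92 day in the second.

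**Dropping the +1 from the timed rule alone.** The first three stays become 0.5 against 1, 2.5 against 3, and 7.5 against 9. Date-only values would then exceed timed ones by 1.00 or 0.92 day on average.

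**Midday imputation for missing times.** A same-date stay with both times missing becomes 12:00 to 12:00, or 0 days.

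**The case against.** Three defences deserve an answer.

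*The SAP uses one inclusive-day convention throughout.* The +1 is in every rule, and it keeps the timed and date-only rules aligned on average. This stands. A reader might infer that only stays with known times are overstated, or that the +1 produces the mismatch. The documents support neither: date-only stays also run about a day above elapsed time, and the mismatch comes from time of day. But an inclusive count needs whole dates, and the general rule specifies date and time.

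*Fractions are not stated.* SAP 4.6.6 does not say whether a timed LOS keeps decimals. SAP 5.9 sets rounding for months and hours but not for days, and SAP 4.6.7 counts days to re-anticoagulation with a calendar-day function. If timed stays were counted that way, the 10:00 to 22:00 stay would be 1 day under both rules and the problem would vanish. This is possible. Yet the rule for missing times restricts the calculation to the date part, which implies that the general rule uses the clock. Reading the 1 as one hour is also possible, but the 1-day rule makes it unlikely.

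*The use of LOS is minor.* A reader might infer that the thrombotic-event comparison is off by a day. It is not: a constant added to both groups cancels in a difference of means or medians and leaves ranks unchanged. SAP 5.16.4 names neither a test nor a ratio for LOS. A ratio would be altered (true stays of 10 and 5 days: 10/5 = 2.00, but 11/6 = 1.83), though none is planned.

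**Conclusion.** The general rule is wrong as written, with small consequences. On the reading in days with fractions kept, every timed LOS is 24 hours above the elapsed stay and is not a calendar-day count. The same stay can change by up to just under 1 day in either direction according to whether times were recorded, with a mean gap of 0.00 to -0.08 day under the two assumed patterns.

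The harm is to the reported level of LOS, proportionately largest for short stays, and some added noise. How much depends on the LOS distribution and the share of missing times, which the documents do not give. Nothing carries over to a primary endpoint, the sample size, power or alpha.

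The text also leaves a gap. It has no rule for a stay with only one of the two times, and a discharge date filled in under the missing-date rule may well have no clock time.

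**What to change.** Replace the general rule and the two missing-time rules in SAP 4.6.6 with one: for every patient, LOS in whole calendar days equals discharge date minus admission date plus 1, with clock times ignored. This extends the SAP's existing date-only rules to everyone, reproduces their 1 day for a same-date stay, and settles the unit, the rounding and the case of a single missing time. The missing-discharge-date rule and the consent exclusion can stay. Label the variable as inclusive calendar days, since that count averages about a day more than elapsed time.

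Two tempting alternatives should be avoided. Removing the +1 from the timed rule alone would open a systematic gap of about 1 day between timed and date-only stays. Imputing midday would give 0 days for a same-date stay with both times missing.

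The cost is a few lines of SAP text and one derivation. Individual timed values move up or down by less than 1 day (1.5 becomes 1; 8.5 becomes 9), and clock-time precision is lost.
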